6.13.2.2. Analyses of ADA Effects on Efficacy

Efficacy analyses will be conducted on all evaluable patients within the ITT population in Period 2 and on all evaluable patients within the Maintenance Dosing Period Primary Population in Period 3.

sPGA (0), sPGA (0,1), PASI 75, PASI 90 and PASI 100 response rates at Week 12 and 60 (NRI) will be summarized by the TE-ADA status groups. A logistic regression model with treatment group, TE-ADA status group and the interaction of treatment-by-TE-ADA status group included as factors will be used to test the interaction of treatment-by-TE-ADA status group. The p-value associated with the interaction term will be used to assess if the treatment effect is consistent across the TE-ADA status group. When the interaction term is statistically significant, the association between responder status and treatment depends, in some manner, on the TE-ADA status group. The interaction will be tested at the 10% significance level. Treatment group differences will be evaluated within each subgroup using Fisher's exact test regardless of whether the interaction is statistically significant.

The relapse rate (loss of response; sPGA ≥ 3) at Week 60 (NRI) will also be summarized by the TE-ADA status groups for the Maintenance Dosing Period Primary Population.

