6.13.1.1. Sample Category Definitions

Samples are classified into the following categories:

- **Unevaluable sample:** Sample could not be tested for ADA due to sample loss, mishandling, or errors in collection, processing, storage, etc.
- **Anti-drug antibody (ADA) Positive sample:** The presences of ADA is detected and confirmed. The samples are reported as positive. If the sample is positive, a titer value is reported.
- **Neutralizing antibody (NAb) Positive sample:** NAb are reported as detected.
- **ADA Negative sample:** The presence of ADA is not detected and the assay drug tolerance level is not exceeded.
- **NAb Negative sample:** The presence of NAb is not detected and the assay drug tolerance level is not exceeded.
- **ADA/NAb Inconclusive sample:** when ADA/NAb is not detected in a sample but drug is present in the same sample at a level that can cause interference in the ADA/NAb detection method, the negative ADA/NAb result cannot be confirmed and the sample should be considered inconclusive.
 - Confirmation of a negative ADA result was based on ixekizumab concentrations.

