6.13.1.3. Definitions for Clinical Interpretation of Assay Results

- **Baseline:** For immunogenicity analyses during Period 2, baseline is the last nonmissing observation on, or prior to, the date of the first injection of study treatment (Week 0). Unless otherwise specified, the baseline for subsequent treatment periods is defined as the last nonmissing observation on, or prior to, the date of first injection of ixekizumab. For patients originally randomized to ixekizumab during Period 2, baseline is the last non-missing observation on, or prior to, the date of the first injection of study treatment for Period 2 (Week 0). For patients who are originally randomized to placebo in Period 2, baseline is the last non-missing observation on, or prior to, the date of the first injection of ixekizumab. See [Table RHBH. 6.10.](#) for further details.

Table RHBH. 6.10. Definition of Baseline for Immunogenicity Analysis for Maintenance Dosing Period

Period 2 (Induction Period) Randomized Treatment	Week 12 Responder?	Period 3 (Maintenance Dosing Period) Treatment	Relapse (sPGA ≥3)?	Baseline ¹
Ixekizumab	Yes/No	Ixekizumab	Yes/No	Week 0
	Yes	Placebo	Yes/No	Week 0
Placebo	No	Ixekizumab	Yes/No	Week 12
	Yes	Placebo	Yes	Week of Relapse in Period 3
			No	Week 0

Abbreviations: NA = not applicable; sPGA= static Physician Global Assessment.

¹ last nonmissing observation on, or prior to, the date of the first injection of study treatment at the defined Week

- **Baseline ADA positive (preexisting antibody) patient:** ADA detected in a sample collected at baseline.
- **TE-ADA positive patient:** a) a patient with a ≥4-fold (or 2 dilutions) increase over a positive baseline antibody titer; or b) for a negative baseline titer, a patient with an increase from the baseline to a level of ≥1:10.
- **Baseline ADA-negative patient:** ADA is not detected in a sample collected at baseline.
- **TE-ADA inconclusive patient:** A patient without a TE-ADA positive sample and with at least 1 sample for which drug levels may interfere with the ADA assay.
- **TE-ADA negative patient:** A patient who is evaluable for TE-ADA and is not either TE-ADA positive or TE-ADA inconclusive.
- **Incidence of TE-ADA:** Patients with TE-ADA as a proportion of the evaluable patient population during the treatment period. This excludes unevaluable patients.

All ADA positive samples will be evaluated for NAb. Definitions for NAb patient status will be defined as follows:

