6.13.2. Immunogenicity Analyses

Immunogenicity evaluable patients will be identified as TE-ADA positive, TE-ADA negative, or TE-ADA inconclusive, according to the definitions provided in Section 6.13.1.3 and further grouped into TE-ADA status groups and time-varying TE-ADA status groups.

TE-ADA Status Groups:

- TE-ADA status (positive, negative, or inconclusive);
- NAb status (positive, negative, or inconclusive) for TE-ADA positive patients; and
- TE-ADA titer groups for TE-ADA positive patients:
 - Low Titer: TE-ADA titer value (LOCF) <1:160;
 - Moderate Titer: TE-ADA titer value (LOCF) ≥1:160 and <1:1280; and
 - High Titer: TE-ADA titer value (LOCF) ≥1:1280.

Time-Varying TE-ADA Status Groups:

Individual ADA samples will be ascribed into 3 different dichotomous variables as explained in Table RHBH. 6.11. Each variable has possible values of a “greater-TE-ADA status” or a “lesser-TE-ADA status,” in the sense that the level of TE-ADA detected in the greater-TE-ADA category is higher than in the lesser-TE-ADA category.

Table RHBH. 6.11. TE-ADA Status Dichotomous Variables for AE Analysis

TE-ADA Status Dichotomous Variable	Greater-TE-ADA Status	Lesser-TE-ADA Status
TE-ADA positive	TE-ADA positive	not TE-ADA positive
TE-ADA moderate-to-high	TE-ADA positive with moderate titer or high titer	not TE-ADA positive, or TE-ADA positive with low titer
TE-ADA high status	TE-ADA positive with high titer	not TE-ADA positive, or TE-ADA positive with low or moderate titer

Abbreviations: AE = adverse event; TE-ADA = treatment-emergent anti-drug antibody.

Notes: For the purpose of this analysis, TE-ADA Inconclusive is taken to be “not TE-ADA positive.”

A TE-ADA low is defined as a TE-ADA positive with a titer value <1:160; a TE-ADA moderate is defined as a TE-ADA positive with a titer value ≥1:160 and <1:1280; and a TE-ADA high is defined as a TE-ADA positive with a titer value ≥1:1280.

For each TE-ADA status dichotomous variable, a time-varying TE-ADA status will be computed. At time *t*, the TE-ADA status is taken to be the highest of the TE-ADA values bracketing time *t*. More formally, the TE-ADA status at time *t* is given by the greater of (a) the TE-ADA status at the most-recent post-baseline measurement prior to *t*, and (b) the TE-ADA

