6.13.2.1. Analyses of Characteristics of ADA Immune Response

The analyses of ADA effects will be conducted on all evaluable patients within the defined safety population for Induction Dosing Period (Period 2), and Combined Induction and Maintenance Dosing Periods (Combined Periods 2 and 3, information prior to relapse), and for Maintenance Dosing Period Relapse Population in Maintenance Dosing Period.

Baseline definition for immunogenicity analyses for the Combined Treatment Period is the same as [Table RHBH. 6.10](#).

The overall frequency and percentage (incidence) of patients will be summarized for the TE-ADA status groups and the time-varying TE-ADA status groups. Scheduled visits, unscheduled visits, and repeat measurements will be included.

In addition, the overall frequency and percentage (incidence) of patients will be summarized for the patients who are baseline ADA positive by TE-ADA status groups. For those patients who are TE-ADA positive, a summary of titer values and the proportion of patients who are NAb positive will also be provided.

The time to development of TE-ADAs (TE-ADA positive, Low titer, Moderate titer, High titer, and NAb positive) will be calculated as follows:

$$\text{Time to development of TE-ADA/NAb (in weeks)} = (\text{Date of development of TE-ADA/NAb} - \text{Date of first injection of study treatment} + 1) / 7$$

If a patient has not developed TE-ADA/NAb, they will be censored at the date of the last immunogenicity assessment.

A Kaplan-Meier plot of the time to development of TE-ADA/NAb will be presented by treatment group, if sufficient data is present. The log-rank test will be used to test the null hypothesis against the alternate hypothesis that the time to TE-ADA/NAb is not equal between each ixekizumab dose and placebo. Caution should be exercised in the interpretation of time-to-event analyses and related statistics given the limited sampling scheme for immunogenicity testing.

For each TE-ADA status dichotomous variable (as defined in [Table RHBH. 6.11](#).), summaries will be provided of the total post-baseline time in the greater-TE-ADA status for patients who were at some point post-baseline in the greater-TE-ADA status group. Post-baseline time in greater-TE-ADA status for each patient will be aggregated.

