6.14. Subgroup Analyses

6.14.1. Efficacy Subgroup Analyses

Subgroup analysis will be conducted for sPGA (0), sPGA (0,1), PASI 75, PASI 90 and PASI 100 at Week 12 (NRI) using the ITT population for Period 2 and at Week 60 (NRI) using the Maintenance Dosing Period Primary Population for Period 3.

A logistic regression model with treatment, subgroup, and the interaction of subgroup-by-dosing regimen included as factors will be used. The subgroup-by-treatment interaction will be tested at the significance level of 0.10. Treatment group differences will be evaluated within each category of the subgroup using Fisher's exact test, regardless of whether the interaction is statistically significant. Missing data will be imputed using NRI. If any group within the subgroup is <10% of the total population, only summaries of the efficacy data will be provided (that is, no inferential testing).

Please see [Table RHBH. 6.3.](#) for subgroups of baseline characteristics that will be analyzed.

In addition, concomitant topical therapy subgroups will also be analyzed:

- Concomitant topical product use: yes, no
- Concomitant topical steroid product use: yes, no.

Additional subgroup analyses on efficacy may be performed as deemed appropriate and necessary.

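### At Week 12 the treatment-by-TE-ADA interaction test hardly detects an antibody effect shared by both ixekizumab doses, and no analysis in the SAP estimates that effect directly

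*SAP*

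**What the plan says.** SAP 4.2.2 lists the impact of anti-ixekizumab antibodies on efficacy among the other secondary objectives. The efficacy part is in SAP 6.13.2.2. sPGA and PASI response rates at Weeks 12 and 60 are summarised by TE-ADA status group, and then "A logistic regression model with treatment group, TE-ADA status group and the interaction of treatment-by-TE-ADA status group included as factors will be used". The interaction is tested at the 10% level, and "The p-value associated with the interaction term will be used to assess if the treatment effect is consistent across the TE-ADA status group". The section goes on to interpret a significant result. It says nothing about a non-significant one. Whatever the interaction shows, "Treatment group differences will be evaluated within each subgroup using" Fisher's exact test.

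SAP 6.13.2 gives TE-ADA status three levels: positive, negative and inconclusive. Under SAP 6.13.1.1 a sample is inconclusive "when ADA/NAb is not detected in a sample but drug is present in the same sample at a level that can cause interference" with the assay. Under SAP 6.13.1.3 an inconclusive patient is "A patient without a TE-ADA positive sample and with at least 1 sample for which drug levels may interfere with the ADA assay". Placebo patients can in principle be TE-ADA positive, and SAP 6.13.2.1 allows for this by testing whether "the time to TE-ADA/NAb is not equal between each ixekizumab dose and placebo".

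**The concern.** The antibody question is whether patients on ixekizumab who develop antibodies respond less well. The most natural form of that is a loss seen on both doses. The interaction test reaches it only indirectly, by asking whether the ixekizumab-versus-placebo odds ratio differs by TE-ADA status. It therefore depends on placebo patients who are TE-ADA positive, and on responders among them. Both will be scarce at Week 12.

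The within-group Fisher tests also compare treatments, not antibody groups. If the interaction p-value is the stated tool and it is non-significant, a study report could describe the effect as consistent when the data could hardly have shown otherwise.

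**Working it through.** **Inputs from the documents.** 420 patients, 2:2:1, so 168 / 168 / 84 (SAP 5.3). Week 12 response 75% on each ixekizumab dose and 5% on placebo (SAP 5.3). Interaction level 0.10 (SAP 6.13.2.2). Placebo patients receive only placebo through Week 10 (Protocol Table RHBH.9.1), and prior ixekizumab exposure is excluded (Protocol 8.2, criterion 15).

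**The plan's own figure.** Exact Fisher power for 168 versus 84, 75% versus 5%, two-sided 0.025, is above 99.99%. The stated >99% reproduces. No power is stated for the interaction test.

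**Assumptions.** The documents give no TE-ADA rates. I took placebo positive q = 1%, 2%, 5%, 10%; ixekizumab 10% positive and 5% inconclusive; all 420 evaluable; placebo response 5% whatever the antibody status. SAP 6.13.2.2 does not name the test, so I used the likelihood-ratio test.

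**Degrees of freedom, three arms by three levels.** Nominal (3−1)(3−1) = 4. The additive model has 3+3−1 = 5 parameters. Inconclusive needs drug in the sample, so the placebo-by-inconclusive cell is empty barring dosing errors: 8−5 = 3. If no placebo patient is positive either: 7−5 = 2, and those two contrasts compare only Q2W with Q4W.

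**Placebo positives.** Expected number 84q. Chance of none (1−q)^84. Chance that the cell holds both a responder and a non-responder, with p = 0.05: 1 − (1−q(1−p))^84 − (1−qp)^84 + (1−q)^84.

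**Simulation.** 4,000 trials per setting, Monte Carlo SE about 0.5 points. Response in ixekizumab positives falls from 75% to 45% on both doses.

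| Placebo TE-ADA positive (assumed) | 1% | 2% | 5% | 10% |
|---|---|---|---|---|
| Expected placebo positives | 0.8 | 1.7 | 4.2 | 8.4 |
| Chance of none | 43% | 18% | 1.3% | <0.1% |
| Chance cell holds both outcomes | 2% | 6% | 19% | 34% |
| Rejection, three-level status | 12.4% | 12.9% | 13.5% | 16.9% |
| Rejection, inconclusive merged with negative | 10.2% | 11.2% | 13.4% | 15.7% |

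With no antibody effect the three-level test rejects in 10.5% (placebo 2%) and 11.6% (placebo 10%).

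**Cause.** Merging the inconclusive group does not raise the rejection rate, so the empty cell is not the main problem. Expected responders among placebo positives are 84 × 0.02 × 0.05 = 0.08 at q = 2% and 84 × 0.10 × 0.05 = 0.42 at q = 10%. There is almost nothing to compare against.

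**Other shared-loss settings.** At placebo 2%, a fall to 20% response gives 14.6%. With 5%, 15% or 20% positive on ixekizumab, a fall to 45% gives 13.3%, 12.5% and 12.3%. A separate grid (placebo 1% to 5%, 1,000 runs per setting) never exceeded about 25%, even with response in positives reduced to the placebo rate of 5%. An approximate Wald test on that grid gave 1% to 22%.

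**Loss on one dose only.** At placebo 2%, with only Q4W positives affected, rejection is about 39% for a fall to 45% and 83% to 85% for a fall to 20%.

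**Direct comparison within ixekizumab.** Half-width of the 95% CI = 1.96 × √(0.45×0.55/n_pos + 0.75×0.25/n_neg), 336 patients, 5% inconclusive excluded:
- 5% positive (16.8 v 302.4): 24 points
- 10% positive (33.6 v 285.6): 18 points
- 20% positive (67.2 v 252): 13 points

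Comparing positives with all other ixekizumab patients (Fisher, 0.10), power for 50% versus 75% is 69%, 89% and 98% at those rates.

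**The case against.** **The test is not powerless.** A dose-dependent antibody effect is one form of inconsistency, and the test can detect it, as the one-dose figures show. A reader might infer that it is uninformative in general. That would be wrong: the weakness is against a loss shared by both doses. Even there, if 20% of placebo patients were positive, power would reach about 55% for complete loss of effect. This limits the point.

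**The SAP does not make the bad inference.** A reader might take 6.13.2.2 to say that a non-significant interaction shows consistency. It does not; it interprets only significance. The risk lies in reporting, and a sentence would deal with it.

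**The reduced degrees of freedom do no shown harm.** The test stays near its nominal level under no effect. The count of 3 also holds only for the three-arm model with three-level status and some inconclusive patients. The titre and neutralising-antibody groupings give other counts, and a misdosed placebo patient could fill the cell.

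**Other safeguards.** SAP 6.14.1 states: "If any group within the subgroup is <10% of the total population, only summaries of the efficacy data will be provided". That rule is not written into 6.13.2.2. If it were applied, a 5% inconclusive rate would give 336 × 0.05 / 420 = 4.0% and stop testing, which still leaves the antibody question unanswered. The sparse-data fallback to Fisher's test in SAP 6.1.2 does not test an interaction. Response by TE-ADA status is already summarised, and Protocol 12.2.7 allows graphs of exposure by antibody status. PK/PD detail is in a separate plan not available here.

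**Conclusion.** The concern holds in limited form and is minor. At Week 12 the interaction test rejects about 12% to 17% of the time for a 30-point fall in response shared by both doses, against about 10% to 12% with no effect. A non-significant result therefore says little about whether antibodies reduce response on ixekizumab. Neither the protocol nor the SAP plans an estimate with a confidence interval for antibody-positive versus antibody-negative patients on ixekizumab, although the objective calls for that information.

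The size rests on assumed antibody rates, SAP 5.3 response rates, full evaluability and the likelihood-ratio test. The empty placebo-by-inconclusive cell follows from the documents.

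A reader might extend the point to Week 60. The structural argument does not carry over, because re-randomised placebo patients had ixekizumab in Period 2. Primary and major secondary conclusions are unaffected.

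**What to change.** Keep the planned summaries and tests. In SAP 6.13.2.2, for Week 12:

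- Add the difference in response between TE-ADA positive and negative patients within the ixekizumab arms, with regimen as a factor and a 95% CI, labelled observational.
- Show the inconclusive, titre and neutralising-antibody groups descriptively.
- State that a non-significant interaction is not evidence of a consistent effect, particularly against a loss shared by both doses.

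The cost is SAP wording and one extra analysis on existing data. The downside is that the comparison is not randomised, and it will be imprecise if few patients are positive, as the half-widths above show.

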6.13.2.3. Analyses of ADA Effects on Specific Adverse Events

The analyses of ADA effects on safety will be conducted on all evaluable patients within the defined safety population for Period 2 and Combined Induction and Maintenance Dosing Periods (Combined Periods 2 and 3, information prior to relapse).

Baseline definition for immunogenicity analyses for the Combined Treatment Period is the same as [Table RHBH. 6.10](#).

AESIs of allergic reaction/hypersensitivity (anaphylaxis and non-anaphylaxis) and of injection site reactions will be included in an assessment of AE to TE-ADA over time. Timing of an AE will be taken to be the reported AE start date.

For each TE-ADA status dichotomous variable (as defined in [Table RHBH. 6.11](#).), patients will be categorized according to whether they were (i) always in lesser-TE-ADA status post-baseline or (ii) at some point post-baseline were in greater-TE-ADA status. For each AESI, within the time-varying TE-ADA status groups, a summary will be provided of the number of patients who had no event, events only while in lesser-TE-ADA status for group (i), or – for group (ii) – at least 1 event while in greater-TE-ADA status.

Additionally, summaries will be provided of the total number of AESI events (with unique start dates) by time-varying TE-ADA status groups at the event date. The summaries will aggregate time respectively, in greater-TE-ADA status and in lesser-TE-ADA status, along with the event rates (rates per 100 patient-years) relative to those aggregate times.

By-patient listings will be provided of patients with TE-ADA who experience a treatment-emergent allergic reaction/hypersensitivity reaction or an injection site reaction.

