### **7.1.2. Induction Dosing Period (Period 2)**

The Induction Dosing Period (Period 2) will be a double-blind treatment period that will occur from Week 0 (baseline; Visit 2) to Week 12 (Visit 7); dosing will occur Q2W from Weeks 0 to 10 and evaluation of primary endpoints will occur at Week 12 prior to the Week 12 dose.

At Week 0 (baseline; Visit 2), routine safety assessments, laboratory tests, and clinical efficacy assessments will be performed on eligible patients according to the Study Schedule ([Attachment 1](#)).

Patients will be randomized at a 2:2:1 ratio to 1 of 3 treatment groups: 80 mg ixekizumab Q2W, 80 mg ixekizumab Q4W, or placebo. Each patient assigned to an ixekizumab dose regimen will receive a starting dose of 160 mg ixekizumab as 2 SC injections at Week 0 (Visit 2).

Blinded dosing will occur at 2-week intervals throughout Period 2. See Section 9.1 and [Table RHBH.9.1](#) for a full description of all treatment groups. To maintain blinding, each patient will be administered 2 injections of blinded investigational product subcutaneously at Week 0, and each patient will be administered 1 injection of blinded investigational product subcutaneously Q2W from Weeks 2 through 10 regardless of his/her assigned dose regimen (that is, placebo will be given as necessary to maintain the blind).

Patients who discontinue the study for any reason during this period will stop treatment and continue to the ETV prior to entering the Post-Treatment Follow-Up Period (Period 4; Section 7.1.4).

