### **7.1.3. Maintenance Dosing Period (Period 3)**

The Maintenance Dosing Period (Period 3) will be a double-blind treatment period that will occur from Week 12 (Visit 7) to Week 60 (Visit 19).

In Period 3, safety and efficacy parameters in participating patients will continue to be evaluated according to the Study Schedule ([Attachment 1](#)).

Two treatment groups (80 mg Q4W and placebo) will be evaluated to determine the maintenance of response/remission, the relapse or rebound following treatment withdrawal, and the response to retreatment following relapse (see “Treatment Assignment for Responders” and “Non-responders” below).

Blinded dosing will occur at 4-week intervals throughout Period 3. See Section 9.1 and [Table RHBH.9.1](#) for a full description of all treatment groups. To maintain blinding, each patient will be administered 2 injections of blinded investigational product subcutaneously at Week 12, and each patient will be administered 1 injection of blinded investigational product subcutaneously Q4W from Weeks 16 through 56 (Week 60, no investigational product administration) regardless of his/her assigned treatment group (that is, placebo will be given as necessary to maintain the blind).

At Week 12 (Visit 7), patients who enter Period 3 will be classified as a responder or non-responder according to the following criteria:

- **Responder = sPGA score of “0” or “1”**
- **Non-responder = sPGA score of > 1**

**Treatment Assignment for Responders:** Patients receiving ixekizumab who are responders at Week 12 (Visit 7), will be re-randomized (2:1) to 2 treatment groups (80 mg ixekizumab Q4W or placebo). Patients will be stratified by ixekizumab induction dosing regimen (80 mg Q2W or 80 mg Q4W).

Patients randomized to placebo at Week 0 (Period 2) who are responders at Week 12 (Visit 7) will continue to receive placebo at 4-week intervals during Period 3 until relapse; these patients will receive 2 SC injections of placebo at Week 12 (Visit 7) in order to maintain the study blind.

All treatments will remain in effect until relapse. Relapse (loss of response) is defined as an sPGA score of  $\geq 3$ .

**Treatment Following Relapse:** Patients who are responders at Week 12 will be monitored and assessed for relapse at each visit after re-randomization. Patients who relapse will be treated as follows:

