6.8. Treatment Compliance

By-patient listings of randomization schedule for the ITT population and study drug dispensed (include the CT Lot number) for the Safety Population will be provided.

Throughout the treatment period, randomized patients will record information in a Study Drug Administration Log (captured in the *Exposure as Collected* eCRF page), including the date, time, and anatomical location of administration of investigational product, syringe number, who administered the investigational product, and the reason if the investigational product was not fully administered.

Treatment compliance for each patient will be calculated as:

$$\text{Treatment compliance (\%)} = 100 \times \frac{\text{Total number of injections administered}}{\text{Total number of injections prescribed}}$$

- For patients who complete Period 2, the number of injections prescribed (that is, expected) during Period 2 will be equal to 7 (2 injections at Week 0 and 1 injection every 2 weeks from Week 2 to Week 10).
- For patients who complete Period 3, the number of injections prescribed (that is, expected) during Period 3 will be equal to 13 (2 injections at Week 12 and 1 injection every 4 weeks from Week 16 to Week 56).
- For patients who discontinue during the treatment period, the number of injections prescribed can be derived from the IWRS study drug dispense dataset.
- The total number of injections administered will be derived using the response to the question “Was dose administered?” on the *Exposure as Collected* eCRF page.

A patient will be considered overall compliant with study treatment during each treatment period if he/she misses no more than 20% of the expected doses, does not miss 2 consecutive doses, and

does not over-dose (that is, take more injections at the same time point than specified in the protocol).

Treatment compliance by treatment week and overall will be summarized for the Safety Population for Period 2 and for the Maintenance Dosing Period Primary/Secondary Population for Period 3.

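### SAP 6.13.2.3: the combined-period injection-site reaction rate by TE-ADA status mixes two injection frequencies; separately, the patient counts omit ever-positive patients whose events all fell in lesser status

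*SAP*

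**What the plan says.** SAP 6.13.2.3 is "conducted on all evaluable patients within the defined safety population", once for Period 2 and once for Periods 2 and 3 combined, using information before relapse. It covers injection-site reactions and allergic/hypersensitivity events and produces two different summaries.

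- **Event rates.** All events are classified by TE-ADA status on the event date: "The summaries will aggregate time respectively, in greater-TE-ADA status and in lesser-TE-ADA status, along with the event rates (rates per 100 patient-years"). The section names no split of the combined window by period and no per-injection denominator.
- **Patient counts.** Patients are divided into (i) always in lesser status after baseline and (ii) in greater status at some point. The categories are no event, "events only while in lesser-TE-ADA status for group (i), or – for group (ii) – at least 1 event while in greater-TE-ADA status".

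Under SAP 6.13.2, status at any time is the higher of the samples on either side, so positivity is backdated to the previous sample. Before the first post-baseline sample, that sample's value applies. Protocol Attachment 1 schedules immunogenicity samples at Weeks 0, 2, 4, 12, 24, 36 and 60.

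On dosing, SAP 6.8 gives the Period 2 injection count as "will be equal to 7 (2 injections at Week 0 and 1 injection every 2 weeks from Week 2 to Week 10") and the Period 3 count as "will be equal to 13 (2 injections at Week 12 and 1 injection every 4 weeks from Week 16 to Week 56"). The change applies to every arm. In Protocol 7.1.2 each patient gets "1 injection of blinded investigational product subcutaneously Q2W from Weeks 2 through 10 regardless of his/her assigned dose regimen"; in Protocol 7.1.3, "each patient will be administered 1 injection of blinded investigational product subcutaneously Q4W from Weeks 16 through 56".

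**The concern.** An injection-site reaction can only follow an injection, so patient-time is a fair exposure measure only while injection frequency is constant. In the combined window it roughly halves at Week 12. If greater-status time falls mainly after Week 12 while lesser-status time includes Weeks 0-12, the two rates differ because of the schedule alone. A reader could take that difference for an effect of antibodies on safety, which is what the secondary objective in SAP 4.2.2 asks about.

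The patient counts have an unrelated gap. The lesser-only category is written for group (i) alone. A group (ii) patient whose events all came in lesser status fits none of the categories.

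**Working it through.** **Plan's own figures.** Period 2: 2 + 5 = 7 injections on 6 dosing days. Period 3: 2 + 11 = 13 injections on 12 dosing days. Both totals match SAP 6.8.

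**Intensity** (365.25/7 = 52.18 weeks per year).
- Period 2: 7/12 × 52.18 = 30.4 injections per patient-year (26.1 dosing days).
- Period 3: 13/48 × 52.18 = 14.1 (13.0 dosing days).
- Period 3 to Period 2: 0.46 by injection, 0.50 by dosing day.

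**Null calculation.** Event risk is the same per injection (or per dosing day) whatever the TE-ADA status. From the documents: 168 + 168 = 336 ixekizumab patients; 84 × 0.95 ≈ 80 placebo non-responders, counted from Week 12 because SAP Table RHBH 6.10 puts their baseline there; the sampling weeks; and the bracketing rule. Assumed: 20% TE-ADA positive (10% and 30% change the ratios very little), with onset and persistence varied. The 80 are kept in lesser status throughout.

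*Example: persistent, first positive at Week 24.* Backdating puts greater status at Weeks 12-60. Positive patients: 0.2 × 336 = 67.2; never positive: 268.8.
- Greater: 13/48 per week = 14.1 per year.
- Lesser injections: 268.8 × 20 + 67.2 × 7 + 80 × 13 = 6886.4.
- Lesser weeks: 268.8 × 60 + 67.2 × 12 + 80 × 48 = 20774.4.
- Lesser rate: 6886.4/20774.4 × 52.18 = 17.3 per year.
- Ratio: 14.1/17.3 = 0.82.

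Greater/lesser null ratios, combined window (risk per dosing day / per injection):

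| First positive sample | Persistent | Positive at that sample only |
|---|---|---|
| Week 2 | 1.03 / 1.04 | 1.73 / 2.35 |
| Week 4 | 1.00 / 0.95 | 1.75 / 1.57 |
| Week 12 | 0.97 / 0.93 | 1.21 / 1.25 |
| Week 24 | 0.84 / 0.82 | 0.85 / 0.90 |
| Week 36 | 0.84 / 0.75 | 0.84 / 0.75 |
| Week 60 | 0.85 / 0.76 | 0.85 / 0.76 |
| Spread evenly | 0.94 / 0.90 | 1.02 / 1.00 |

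**Sensitivity.** Without the 80 placebo non-responders, which approximates showing an ixekizumab arm on its own, late persistent onset gives 0.73-0.82. Stopping follow-up at relapse 8-24 weeks after re-randomisation, for an assumed 90% of the roughly 78 patients re-randomised to placebo, moves the late persistent ratios by about 0.02.

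**Period 2 alone.** The null ratio is 1.00 per dosing day and 0.84-1.00 per injection. The only source of difference is the double injection at Week 0.

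**Patient counts.** Let a positive patient have m of 18 dosing days in lesser status and event risk p per dosing day. The chance of landing in the missing category is (1 − (1 − p)^m) × (1 − p)^(18 − m). With p = 2% (assumed) and persistent antibodies: 1.4% of group (ii) for Week 4 onset (m = 1), 9.0% for Week 24 (m = 6) and 19.1% for Week 60 (m = 12). Over p = 1-5% the range is about 1% to 34%.

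**The case against.** The strongest case against has five parts.

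- **The direction is not settled.** Backdating and three early samples make early persistent positivity almost neutral, and early transient positivity reverses the sign. This stands. A reader might infer that reactions must look rarer once antibodies appear; the documents do not support that, because they give no TE-ADA incidence, onset or persistence. What remains is that a ratio away from 1 cannot be interpreted from the planned output.
- **Period 2 is already analysed alone.** This stands, and it confines the problem to the combined window. It is also confined to injection-linked events; hypersensitivity need not follow injection frequency.
- **Results are shown by treatment group.** SAP 6.12.2, 6.12.3.1 and Table RHBH 6.1 point that way. This answers any worry that placebo-arm time is silently pooled into lesser status. It does not remove the mixing, because every arm changes frequency at Week 12.
- **The missing count is recoverable.** The group (ii) total in SAP 6.13.2.1, less the two reported categories, gives it, and by-patient listings of reactions in TE-ADA patients are planned. True, but the table would still not add up as specified.
- **The summaries are descriptive.** No test or decision rule depends on them. This stands and sets the severity.

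**Conclusion.** There are two separate, minor defects.

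First, the combined-period patient-year rate for injection-site reactions pools time at about 30 and about 14 injections per patient-year. Under no antibody effect the greater/lesser ratio is about 0.75-0.85 for persistent antibodies first seen at Week 24 or later, 0.93-1.04 for early persistent ones, and about 1.2-2.4 for early transient ones. The injection counts come from the plan. The antibody pattern and constant risk per injection or dosing day are assumptions.

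Second, the group (ii) patient counts do not sum. That follows from the wording and needs no assumption; only the size of the gap does.

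Two stronger readings should not be drawn. A reader might link the defects and conclude that the missing category biases the rates. It does not: the rates count every event by status on its date and leave nobody out. The category drops lesser-status patients from a different summary, which if anything would make reactions look rarer before antibodies. Nor do the documents support excluding the placebo arm or time after re-randomisation to placebo. Those patients still receive injections on the common schedule, their data stop at relapse, and separate treatment groups are planned.

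**What to change.** In SAP 6.13.2.3:

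1. For injection-site reactions in the combined analysis, also report events per 100 injections by TE-ADA status on the injection date. Alternatively, add a Weeks 12-60 pre-relapse rate beside the Period 2 rate already planned. Present either by treatment group. Under constant risk the per-injection ratio is 1.00 by construction. The by-period ratio is 1.00 per dosing day, with some residue from the double injections at Weeks 0 and 12 if risk is per injection. A per-injection rate does not correct for a risk per injection that itself changes over time.
2. Add the patient-count category: group (ii), events only while in lesser-TE-ADA status.

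The cost is SAP wording and a little extra programming. Injection dates are already captured in the Study Drug Administration Log (SAP 6.8), so no new data are needed.
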